ANA Anti-Nuclear Antibody

ATC Anatomical Therapeutic Chemical

BMI Body Mass Index

BOA Biostatistical Output Assembly
CDAI Clinical Disease Activity Index

CI Confidence Interval

C_{max} Maximum Serum Concentration

CRP C-reactive protein

CTMS Clinical Trial Management System

CTP Clinical Trial Protocol
CSR Clinical Study Report

Ctrough Serum Concentration

CV% Coefficient of Variation

DAS28-ESR Disease Activity Score Based on a 28 Joint Count

DBP Diastolic Blood Pressure

dsDNA Double stranded deoxyribonucleic acid

eCRF Electronic Case Report Form
EMA European Medicines Agency

ECG Electrocardiogram

EQ-5D-5L European Quality of Life 5-dimensions and 5-levels questionnaire

ESR Erythrocyte Sedimentation Rate

ETA Greek letter η

MSB11022 MSB11022 in Moderate to Severe Rheumatoid Arthritis

MS200588-0004 version 3.0 Final

EULAR European League Against Rheumatism

FDI Functional Disability Index

GBSOS Global Biostatistics Output Standards

GCP Good Clinical Practice

HAQ-DI Health Assessment Questionnaire Disability Index

ICH International Council on Harmonisation
IDDI International Drug Development Institute
IDMC Independent Data Monitoring Committee

IMP Investigational Medicinal Product

ITT Intent-to-Treat

IWRS Interactive Web Response System

LLOQ Lower Limit of Quantification
LTBI Latent Tuberculosis Infection

MedDRA Medical Dictionary for Regulatory Activities

MCS Mental Component Score
NAb Neutralizing Antibodies

NCI-CTCAE National Cancer Institute – Common Terminology Criteria for Adverse

Events

PCS Physical Component Score

PGA Physician's Global Assessment

PK Pharmacokinetic(s)

PP Per-Protocol

PT Preferred Term

QoL Quality of Life

RA Rheumatoid Arthritis
SAE Serious Adverse Event
SAF Safety Analysis Set

SAP Statistical Analysis Plan

sc Subcutaneous

SD Standard Deviation

SDAI Simplified Disease Activity Index

SDTM Study Data Tabulation Model

MSB11022 in Moderate to Severe Rheumatoid Arthritis

MS200588-0004 version 3.0 Final

SEM Standard Error of the Mean

SF-36 36-item Short Form Health Survey

SJC Swollen Joint Count

SMQ Standardized MedDRA Query

SOC System Organ Class

SBP Systolic Blood Pressure

TB Tuberculosis

TJC Tender Joint Count

T_{max} Time To Reach Maximum Serum Concentration

TNF Tumor Necrosis Factor

TEAE Treatment Emergent Adverse Event

ULOQ Upper Limit of Quantification

VAS Visual analogue score

WHODrug World Health Organization Drug

4 Modification History

Unique Identifier for SAP Version	Date of SAP Version	Author Changes from Previous Vers	
Draft 0.1	27 January 2017	PPD	N/A - original
Draft 0.2	24 February 2017	PPD	Sponsor comments incorporated
Draft 0.3	28 April 2017	PPD	Sponsor comments incorporated
Draft 0.4	11 August 2017	PPD	Sponsor comments incorporated Updated as per Protocol amendment 2
Draft 0.5	06 October 2017	PPD	Sponsor comments incorporated
Final 1.0	08 December 2017	PPD	Sponsor comments incorporated
Final 2.0	29 June 2018	PPD	New cutoff rule for Final analysis added
Final 3.0	06 September 2018	PPD	Update to take into account one unique database lock after 4-month safety follow-up

5 Purpose of the Statistical Analysis Plan

The purpose of this statistical analysis plan (SAP) is to document technical and detailed specifications for the analysis of data collected for protocol MS200588-0004. Results of the analyses described in this SAP will be included in the Clinical Study Report (CSR). The CSR will include the 4-week safety follow-up visit (including Week 52 data analysis) and the 4-month safety follow-up visit. Any post-hoc or unplanned analyses performed to provide results for inclusion in the CSR but not identified in this prospective SAP will be clearly identified in the given CSR. Additionally, the planned analyses identified in this SAP will be included in future manuscripts.

The SAP is based upon Section 8 (Statistics) of the Clinical Trial Protocol (CTP) Version 2.0, dated 11 July 2017. It is prepared in compliance with the International Council on Harmonisation (ICH) E9.

The Independent Data Monitoring Committee (IDMC) SAP is also included in this document in Section 18.

6 Summary of Clinical Trial Features

Objectives:

Primary objective

The primary objective of this study is to evaluate the safety profile of MSB11022-CCI

compared to Humira in patients with moderately to severely active rheumatoid arthritis (RA) up to Week 52.

Secondary objectives

The key secondary objective is to compare the efficacy of MSB11022-ccl to Humira at Week 12 in patients with moderately to severely active RA.

Other secondary objectives include:

- To evaluate the immunogenicity profile of MSB11022-cc compared to Humira in patients with moderately to severely active RA up to Week 52
- To compare quality of life (QoL) and physical function on MSB11022-cci with Humira in patients with moderately to severely active RA
- To compare injection site pain levels of MSB11022-cc versus Humira

Exploratory objective

The exploratory objective is to evaluate population pharmacokinetics (PK) of MSB11022-CCI and Humira in patients with moderately to severely active RA

Methodology: This trial is a two-arm, randomized, multicenter, double-blind, parallel group trial designed to compare the safety, immunogenicity, and efficacy of MSB11022-ccl with Humira in approximately 260 randomized patients with moderately to severely active RA during a 52 week period.

Baseline is defined as the day on which the first dose of the investigational medicinal product (IMP) (blinded study drug) is administered (Week 0). The trial will include a pre-trial evaluation period (screening period, from 28 days to 3 days prior to drug administration), a double-blind 48-week treatment period, a 4-week safety follow-up visit, and a 4-month safety evaluation period. The primary safety endpoint will be assessed up to Week 52, key secondary efficacy endpoint will be assessed at Week 12.

Re-screening will be allowed once for those patients who do not meet the inclusion/exclusion criteria within the above specified time limits. The Medical Monitor must promptly inform the Sponsor about requests and reasons for re-screening. An IDMC will review the safety data from this trial on an ongoing basis.

Eligible patients will be randomized in permuted blocks in a 1:1 ratio by an interactive web response system (IWRS) to receive either MSB11022-CCI subcutaneous (sc) or Humira sc at a dose of 40 mg every other week starting at baseline up to and including Week 48. Randomization will be stratified by the type of systemic therapy previously received: non-biological (biologic naïve patients) versus biological (biologic experienced patients). Patients who previously received both (biological and non-biological systemic therapies) will be assigned to the "biological" group. The exposure to previous biological agents will be limited to one tumor necrosis factor (TNF) inhibitor other than adalimumab. The

MSB11022 in Moderate to Severe Rheumatoid Arthritis version 3.0 Final

participation of patients in the previous biological systemic therapy stratum will be capped at 20% of the total number of patients randomized. Capping will be enforced through application of an IWRS.

The first 2 doses of IMP will be administered on site by the Investigator or other qualified personnel and the patient will be educated on the correct process. The third dose of IMP will be administered on-site by the patient. Patients will be monitored for 1 hour following the first 3 IMP administrations. If the Investigator judges it appropriate after proper training, the patient (or a caregiver) may continue to self-inject/inject the treatment for the remaining doses. Injection site pain will be assessed after doses 3 to 5. If a patient self-administers, the injection should not be given in the arm. The remaining doses of IMP will be dispensed, and written instructions on proper dosage, administration, storage, and recording will be provided to the patient/care-giver. Administrations performed at home will be recorded in a diary with the accurate dosing information (dosing date and time).

The 52-week double-blind period will allow for the collection of long-term comparative safety, immunogenicity, and efficacy data for MSB11022-CCI versus Humira.

Subjects who achieve less than a 20% improvement in both swollen and tender joint counts at Week 24 (non-responders) will be discontinued from the IMP. These subjects will remain in the trial safety analysis set and participate in the safety and immunogenicity assessments. After Week 24, patients with less than 20% improvement in both swollen and tender joint counts at any scheduled visit up to Week 52 will also be discontinued. Subjects may continue at Investigator discretion from Week 24 to Week 52 as long as they maintain 20% or more improvement in both swollen and tender joint counts.

Patients who discontinue from study medication (but remain in the trial and continue for the safety/immunogenicity visits) before the Week 52 visit will immediately complete an Early Termination visit and return for a Safety/Follow-up visit four weeks after the last dose of IMP. During this 4-week Safety Follow-up period, no excluded treatment for RA (as defined in the protocol) should be administered. Patients will return for an additional safety evaluation four months after the last dose of IMP. Treatment for RA from the 4-week Safety Follow-up visit to the 4-month Safety Evaluation visit will be at the discretion of the Investigator following institutional standard of care. The 4-week and 4-month Safety Follow-up visits will not be duplicated if either of these visits falls within two weeks of an otherwise scheduled visit. If the 4-week and 4-month Safety Follow-up since last IMP are completed within the 52 week visit schedule, these will not be repeated thereafter.

All subjects will have PK samples taken pre-first dose, and then prior to dosing on Weeks 2, 4, 12, 24, 36 and 52. In addition, a subset of 60 subjects (30 per arm) will have additional samples to support the population PK analysis taken on Days 2 (24 h post first dose), 4, and 9, and Days 2 (24 h post Week 24 dose), 4, 9, and 14 (Week 26 pre dose) after the Week 24 dose.

The anticipated duration of the entire trial is approximately two years.

Visit schedules for safety, immunogenicity, and efficacy assessments are detailed in the

Schedule of Assessments in the protocol.

Planned number of patients: Approximately 260 randomized subjects

Primary endpoint:

• Treatment-emergent adverse events of special interest (AESI) including and up to Week 52

Secondary endpoints:

Key secondary endpoint

• American College of Rheumatology 20% response criteria (ACR20) at Week 12. An ACR20 response is defined as an improvement of at least 20% in the number of tender joints and swollen joints, and at least 20% improvement in three out of the remaining five ACR core-set measures: patient assessment of arthritis pain, Patient's and Physician's Global Assessment of Disease Activity, physical function via the Health Assessment Questionnaire-Disability Index [HAQ-DI] and acute-phase reactant as measured by C-reactive protein (CRP).

Other secondary endpoints

Safety

- Occurrences of treatment-emergent adverse events (TEAEs) and serious adverse events (SAEs) including and up to Week 52
- Clinical laboratory values including hematology, chemistry, and urinalysis
- Vital signs
- Physical exam
- 12-lead electrocardiogram (ECG)

Immunogenicity

- Anti-drug Antibody (ADA) to adalimumab and ADA titer including and up to Week 52
- Neutralizing antibodies (NAbs) to adalimumab including and up to Week 52

Efficacy

- ACR20 at Weeks 2, 4, 8, 24, and 52
- American College of Rheumatology 50% Response Criteria (ACR50) and American College of Rheumatology 70% Response Criteria (ACR70) at Weeks 2, 4, 8, 12, 24, and 52
- Disease Activity Score based on a 28 joint count DAS28-ESR mean change from baseline at Weeks 2, 4, 8, 12, 24, and 52
- Proportion of patients with low disease activity as measured by DAS28-ESR, and remission at Weeks 2, 4, 8, 12, 24, and 52
- Clinical Disease Activity Index (CDAI) and Simplified Disease Activity Index (SDAI)

mean change from baseline at Weeks 2, 4, 8, 12, 24, and 52

• ACR/European League Against Rheumatism (EULAR) Boolean remission rates at Weeks 2, 4, 8, 12, 24, and 52

Quality of life

- HAQ-DI questionnaire at screening, baseline, and Weeks 2, 4, 8, 12, 24, and 52
- 36-item Short Form Health Survey (SF-36) questionnaire at baseline and Weeks 12, 24, and 52
- Euro-Quality of Life 5 Dimensions and 5-levels (EQ-5D-5L) questionnaire at baseline and Weeks 12, 24, and 52

Injection-site pain

• Mean change in injection site pain on a visual analog scale (VAS), evaluated during three administrations of IMP (doses 3 to 5) (immediately post-injection, 15 minutes post-injection, and 1 hour post-injection)

Exploratory endpoints

Population pharmacokinetics

- Absorption profile characterization, if it is supported by the data
- Apparent clearance (CL/F)
- Volume of distribution (Vz/F)
- C_{trough} levels at Day 14 after first dose, at Week 4, 12 and 24 pre-dose, and at Day 14 after dose of Week 24

Planned trial and treatment duration per subject: The planned trial duration per subject is approximately 17 months: a screening period of 28 days to 3 days prior to IMP administration, a double-blind 48-week treatment period to evaluate long-term safety and immunogenicity, a safety follow-up visit four weeks after the last dose of IMP, and an additional safety evaluation at four months following the last dose of IMP. During the 4-week Safety Follow-up period, no excluded treatment for RA (as defined in the protocol) should be administered. Treatment for RA from the 4-week Safety Follow up visit to the 4-month Safety Evaluation visit will be at the discretion of the Investigator following institutional standard of care.

7 Sample Size/Randomization

7.1 Sample Size

According to the European Medicine Agency (EMA) recommendation (EMA/CHMP/SAWP/200743/2016), a total of 100 patients/arm should be adequate for a study primarily focusing on safety. To account for drop outs, this descriptive study will include 260 randomized patients in total (130/arm) in order to ensure 200 subjects are in the study at Week 52. In fact, based on averaged originator's dropout rates at Week 52, a 20% rate of drop-out overall is included in the sample size calculation (1, 2, 3). This sample size will permit an informative assessment of the

occurrence of most common AESIs (> 1/10) such as injection site reactions and rash with a precision of 12.0% and 9.0% for the AESI incidence of 26.0% and 11.0% respectively (0).

A subset of 60 patients (30 per treatment arm) will be randomly selected across all sites to participate in population PK analysis.

7.2 Randomization

Eligible subjects will be randomized in permuted blocks in a 1:1 ratio by an IWRS to receive either MSB11022-CCI sc or Humira sc at a dose of 40 mg every other week starting at baseline up to and including Week 48.

Randomization will be stratified by previous disease-modifying therapy use. Subjects will be stratified by the type of systemic therapy previously received: non-biological (biologic naïve subjects) versus biological (biologic experienced subjects). Subjects who previously received both (biological and non-biological systemic therapies) will be assigned to the "biological" group. The exposure to previous biological agents will be limited to one TNF inhibitor other than adalimumab. The participation of subjects in the previous biological systemic therapy stratum will be capped at 20% of the total number of subjects randomized.

8 Overview of Planned Analyses

Once the last subject has completed the 4-month safety follow-up visit, the database will be locked. The analysis will be performed using cleaned study data collected in electronic case report form (eCRF) or transferred from laboratories performing laboratory tests and biosample analysis until the date of the 4-month safety follow-up visit of the last subject. Once the data cleaning is complete, a data review meeting will be held prior to the database lock. In addition, no data can be frozen or locked and no randomization code should be unblinded until this Statistical Analysis Plan (SAP) has been approved.

The final analysis will include all data collected during the study up to week 52 date (or end of treatment date+28 days, whichever occurs later) for subjects who completed the study, and theoretical week 52 (ie 52 weeks after first intake) or 4 months safety follow-up visit, whichever occurs first, for subjects who early terminated the treatment.

All AE tables and listings will be re-produced to reflect any additional AEs and any updates to the reported AEs in final analysis. Additionally the concomitant medication and procedure tables and listings will be re-produced to reflect any updates.

In addition, an independent data monitoring committee (IDMC) will review safety and tolerability data of this study on an ongoing basis. The methodology and presentation of results for the IDMC are covered in the IDMC Charter and in Section 18.

9 Changes to the Planned Analyses in the Clinical Trial Protocol

Not applicable.

10 Protocol Deviations and Analysis Sets

10.1 Definition of Protocol Deviations

Protocol deviations occurring during the study will be determined for all enrolled subjects, mainly from the clinical database by either clinical and/or medical review processes, and entered into the Clinical Trial Management System (CTMS).

The mapping of the protocol deviations from the CTMS to analysis will be performed as per the table below:

PD Guidance	CTMS	SAP	SDTM	ADaM	
Minor	Minor	Not required	Not included	Not included	
Important	Major	Important	Important - flagged with PDEVXXX code	Important - flagged with PDEVXXX code	
Priority (subset of Important)	Critical (subset of Major)	Important	Mapped to Important	Mapped to Important	
NA	NA	Clinically Important (lead to exclusion from PP pop)	flagged with PDEVXXX code	additional flag = Y/N in ADDV (may also include conditions not considered to be PD's)	

Important protocol deviations are protocol deviations that might significantly affect the completeness, accuracy, and/or reliability of the study data or that might significantly affect a subject's rights, safety, or well-being.

Important protocol deviations may also be recorded as 'major' protocol deviations in the CTMS but will presented only as important in the analysis output.

Important protocol deviations include:

- Subjects that are dosed on the study despite not satisfying the entry criteria;
- Subjects that develop withdrawal criteria whilst on the study but are not withdrawn;
- Subjects that receive the wrong treatment or an incorrect dose;
- Subjects that receive an excluded concomitant medication;
- Deviation from Good Clinical Practice (GCP).

Clinically Important Protocol Deviations are a subset of important protocol deviations which lead to the exclusion of a subject from the Per-Protocol (PP) analysis set.

The following deviations will be identified and confirmed prior to the partial database lock for the final analysis.

- Important protocol deviations including
 - Deviations from the inclusion and exclusion criteria
 - Deviations post inclusion

Protocol deviations may be identified by the data-managers, clinical and medical staff either by programmed validation checks or data listings/reports or manual verification of data sources.

Some important/major protocol deviation criteria may be identified in the clinical database via biostatistical programs. All important protocol deviations will be documented in SDTM datasets whether identified through sites monitoring, medical review or programming. Important protocol deviations to be identified by programming as well as all clinically important protocol deviations are listed and described in Appendix I. The number and percentage of subjects in the ITT Analysis Set with important protocol deviations leading to exclusion from the PP Analysis Set will be presented by treatment arm and reason for exclusion. All important protocol deviations will be presented in a data listing.

10.2 Definition of Analysis Sets and Subgroups

The following table provides an overview of the analysis sets to be used for the different analyses:

Table 1: Overview of Analysis Set Use

Analyses	Enrolled	ITT	PP	SAF	PK
Disposition					
Before Randomization	✓				
After Randomization		✓			
Analysis Sets	✓				
Reason for exclusion from PP set		✓			
Demographics and Other Baseline Characteristics		✓			
Previous and Concomitant Medications/ Procedures		✓	✓		
Compliance and Exposure			✓	✓	
Key Efficacy: ACR20		✓	✓		
Other efficacy endpoints		✓	✓		
QoL		✓	✓		
Injection site pain		✓		✓	
Immunogenicity				✓	
AESIs				✓	
Other safety data				✓	
Pharmacokinetics				✓	✓

ITT = Intent-to-treat, PP = Per-Protocol, SAF = Safety, PK = Pharmacokinetic

10.2.1 Enrolled Analysis Set

The Enrolled Analysis Set includes all subjects who signed the informed consent form.

10.2.2 Intent-to-Treat Analysis Set

The Intent-To-Treat (ITT) Analysis Set includes all subjects randomly allocated to a treatment, based on the intention to treat "as randomized" principle (ie, the planned treatment regimen rather than the actual treatment given in case of any difference). Subjects will be analyzed according to their randomized treatment.

In the event that subjects are incorrectly stratified, ie subjects are randomized according to the incorrect stratification, these subjects will be analyzed under the randomized treatment but with the correct stratification value.

10.2.3 Per-Protocol Analysis Set

The PP analysis set is defined as a subset of the ITT and will include subjects who are compliant with the Clinical Trial Protocol and do not meet criteria that could impact the key objective of the study.

Subjects will be analyzed according to their randomized and received treatment, as receipt of a different treatment from that assigned is an important protocol deviation.

Subjects who meet one of the following criteria will be excluded from the PP set:

- Incorrect treatment group allocation, different to assignment at randomization.
- Unavailability of measurements of the key secondary endpoint.
- Non-compliance with key entry criteria.
- Presence of clinically important protocol deviations.
- Not adequate compliance with and not sufficient exposure to study medication;
 - o Drop out before Week 12
 - Not fully compliant to IP administration during the first 12 weeks of treatment(< 80% compliant).
- Incorrect stratification at randomization with respect to previous systemic therapy.

The criteria for exclusion from the PP analysis set are defined in detail in Appendix I.

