### 5.3.1 Inclusion Criteria

1. Must voluntarily give written informed consent. Patients must read and fully understand the Informed Consent Form (ICF) and the requirements of the trial and must be willing to comply with all trial visits and assessments.
2. Moderately to severely active diagnosis of RA with disease duration of at least 6 months from confirmed diagnosis, as defined by the 2010 revised ACR/EULAR 2010 criteria or the 1987 ARA criteria (Criteria of American Rheumatology Association) (present or past).
3. Have moderately to severely active disease despite MTX therapy defined as:
  - a.  $\geq 6$  swollen joints and  $\geq 6$  tender joints (from the 66/68 joint count system) at screening and randomization.
  - b. Either ESR (Westergren)  $\geq 28$  mm/h or serum CRP  $\geq 1.0$  mg/dL at screening.
4. Must have been treated with MTX for a total of at least 12 weeks prior to baseline and must have been on both: a stable route of administration (oral or parenteral) and stable dose of MTX (10 to 25 mg/week) for at least 4 weeks prior to screening.
5. Age 18 and older.
6. Must be adalimumab naïve and must not have received a non-marketed experimental biological agent for their RA in the past, or any biological agent not belonging to the class of TNF inhibitors. Patients who have received no more than 1 TNF inhibitor (either originator or investigational biosimilar candidate that underwent comparison with EU or US reference compounds) other than adalimumab are allowed to participate in the trial.
7. Must have discontinued infliximab (either originator or investigational or approved biosimilar), certolizumab pegol (either originator or investigational or approved biosimilar) or golimumab (either originator or investigational or approved biosimilar) 8 weeks prior to screening, or etanercept (either originator or investigational or approved biosimilar) 4 weeks prior screening.
8. A female patient is eligible to participate if she is not pregnant (see [Appendix A](#)), not breast feeding, and at least one of the following conditions applies:
  - a. Not a woman of childbearing potential (WOCBP) as defined in [Appendix A](#)

OR

- b. A WOCBP who agrees to use a highly effective contraception (ie, methods with a failure rate of less than 1% per year) as detailed in [Appendix A](#) of this protocol 3 months before the start of the first dose of the IMP, during the treatment period, and for at least 5 months after the last dose of the IMP.

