## 8.2 Randomization

Eligible patients will be randomized in permuted blocks in a 1:1 ratio by an IWRS to receive either MSB11022-**CCI** s.c. or Humira® s.c. at a dose of 40 mg every other week starting at baseline up to and including Week 48.

Randomization will be stratified by previous disease-modifying therapy use. Patients will be stratified by the type of systemic therapy previously received: non-biological (biologic naïve patients) versus biological (biologic experienced patients). Patients who previously received both (biological and non-biological systemic therapies) will be assigned to the “biological” group. The exposure to previous biological agents will be limited to 1 TNF inhibitor other than adalimumab. The participation of patients in the previous biological systemic therapy stratum will be capped at 20% of the total number of patients randomized. This is in accord with what registered in other trials with biological agents in different rheumatic indications (64, 65, 66).

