### 8.4.3 Per-Protocol

The Per-Protocol (PP) analysis set includes all randomized and treated patients (hence a subgroup of the ITT analysis set) who do not have any important clinical protocol deviations (67).

Patients will be analyzed according to their randomized and received treatment, as receipt of a different treatment from that assigned is an important protocol deviation.

The following are criteria for inclusion in the PP analysis set:

- Received the randomized treatment;
- Compliance with all entry criteria;
- Absence of important clinical trial protocol violations per regulatory definition;
- Adequate compliance with and sufficient exposure to IMP;

The criteria for the PP population will be defined in detail in the SAP; major protocol violators excluded from the PP analysis set will be identified.

Patients who achieve less than 20% improvement in both swollen and tender joint counts at Week 24 (non-responders) will be discontinued from the treatment. These patients will remain in the trial safety analysis set and participate in the safety and immunogenicity assessments.

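### The SAP drops patients from the per-protocol set solely for a wrong prior-therapy stratum entry, although ITT keeps them with the stratum corrected and no planned per-protocol analysis uses the stratum

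*SAP*

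**What the plan says.** SAP 10.2.3 introduces its exclusions with "Subjects who meet one of the following criteria will be excluded from the PP set", so one criterion is enough. The last bullet is "Incorrect stratification at randomization with respect to previous systemic therapy". It carries no further condition. Separate bullets cover wrong treatment, missing key secondary endpoint, "Non-compliance with key entry criteria", clinically important deviations, and inadequate compliance or exposure.

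For ITT, SAP 10.2.2 treats mis-stratified patients differently: "these subjects will be analyzed under the randomized treatment but with the correct stratification value".

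Protocol 8.4.3 gives four conditions for the per-protocol set: randomised treatment received, "Compliance with all entry criteria", no important violations, and adequate compliance and exposure. Stratification is not named. The same section adds: "The criteria for the PP population will be defined in detail in the SAP".

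Both strata are eligible. Inclusion criterion 6 (Protocol 5.3.1) admits biologic-naive patients and also "Patients who have received no more than 1 TNF inhibitor", provided that it was not adalimumab. Protocol 8.2 states that "participation of patients in the previous biological systemic therapy stratum will be capped at 20% of the total number of patients randomized".

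**The concern.** A per-protocol set is meant to hold patients who followed the protocol closely enough for their outcome to reflect the treatment under comparison. A wrong stratum entry does not alter which product a patient received, whether doses were taken, or whether ACR20 was measured. The patient is still allocated 1:1.

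The per-protocol set is reported beside ITT for ACR20 at Week 12, the other efficacy endpoints and quality of life. In a biosimilar comparison readers will set the two results side by side. If the sets differ partly because of data entry at randomisation, that part of the difference says nothing about adherence. The SAP does not explain why correcting the stratum is enough for ITT but not for the per-protocol set.

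**Working it through.** **Step 1: whom the bullet removes that no other bullet removes.** One criterion is enough, and ineligibility, wrong treatment, non-compliance, early drop-out, missing endpoint and clinically important deviations each have their own bullet. The stratification bullet on its own therefore adds only patients who pass all the other listed tests. Such patients can exist because both strata are eligible.

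**Step 2: whether a per-protocol analysis needs the stratum.** SAP 15.2.1 gives exact intervals per arm and a Newcombe interval for the ACR20 difference, with no stratification factor named. The breakdown by previous systemic therapy is planned for ITT only (SAP 10.2.6, 15.2.1, 15.2.2). The remaining per-protocol efficacy and quality-of-life outputs are summaries by arm. None depends on the stratum.

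**Step 3: patients lost.** The documents give no mis-stratification rate. Assuming 2-5% of the 260 planned patients:

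- 0.02 × 260 = 5.2, about 5
- 0.05 × 260 = 13

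**Step 4: case mix.** Take a true biologic share b = 20% (52 biologic-experienced, 208 naive). Let e_b be the share of biologic-experienced patients entered as naive, and e_n the share of naive patients entered as biologic. Ignoring other exclusions, the share left in the set is b(1 − e_b) / [b(1 − e_b) + (1 − b)(1 − e_n)]. All error rates are assumptions.

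| e_b | e_n | Lost | Biologic / remaining | Share |
|---|---|---|---|---|
| 5% | 5% | 13.0 | 49.4 / 247.0 | 20.0% |
| 10% | 0 | 5.2 | 46.8 / 254.8 | 18.4% |
| 25% | 0 | 13.0 | 39.0 / 247.0 | 15.8% |
| 0 | 5% | 10.4 | 52.0 / 249.6 | 20.8% |
| 0 | 10% | 20.8 | 52.0 / 239.2 | 21.7% |

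Five errors in each direction give 47/250 = 18.8%. The share falls if e_b > e_n, stays if they are equal, and rises if e_b < e_n.

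**Step 5: precision.** The plan gives no precision for ACR20, so I checked the formula on its adverse-event figures (Protocol 8.1). Half-width = 1.96 × √[2p(1 − p)/n] with n = 100 per arm gives 12.16% at p = 0.26 and 8.67% at p = 0.11. These match the stated 12.0% and 9.0% to the whole percent. For ACR20, assume a 60% response rate and 104 per arm (130 × 0.80). The formula is a simple approximation to the Newcombe interval:

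- no loss: 1.96 × √(0.48/104) = 13.3%
- 2% lost (n = 101.92): 13.5%
- 5% lost (n = 98.8): 13.7%

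**The case against.** The best argument for the bullet is the cap. The stratum entry selects the permuted block, and it also drives the 20% limit that the IWRS enforces. Once the limit is reached, a biologic-experienced patient entered as naive is randomised when a correct entry would have stopped it. Stratified randomisation is a protocol procedure, Protocol 8.4.3 bars patients with important deviations, and it leaves the detail to the SAP.

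Part of this stands. It would be wrong to say that the exclusion can serve no purpose at all, or that the SAP contradicts the protocol. But the cap limits recruitment to a stratum; it is not an entry criterion that an individual patient fails. The bullet also removes every mis-entered patient, whether or not the cap was involved. SAP 10.1 separates important deviations from the clinically important subset that leads to exclusion, so the error can be recorded without removing the patient.

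Two stronger readings are tempting, and the documents support neither.

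- A reader might infer that the set shifts toward biologic-naive patients, because a missed prior biologic seems the likelier error. The bullet applies to errors both ways and no direction is given. Protocol 7.2.2 also asks sites to record all past biologic use.
- A reader might take 5-13 losses as 10-25% of the biologic stratum (5/52 and 13/52). That needs every error to run one way and needs 52 to be the ceiling on true biologic-experienced patients. If the cap acts on the entered stratum, miscoded patients do not count toward it. With 52 entered correctly and 13 miscoded, the true number is 65. The fraction lost is then 13/65 = 20%, and exclusion moves the share from 65/260 = 25% to 52/247 = 21%, closer to the planned mix.

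Finally, the loss would be visible: per-protocol exclusions are tabulated by arm and reason (SAP 10.1) and also summarised and listed (SAP 12.1).

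**Conclusion.** The point holds as a minor one. The text of SAP 10.2.3 removes patients for the stratum entry alone, ITT handles the same patients by correction, and no planned per-protocol analysis gains from the exclusion. Valid patients are lost, and case mix can move either way.

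The size is small. About 5-13 patients would be lost under the assumed 2-5% error rate, and the ACR20 half-width would grow by at most about 0.4 percentage points (13.3% to 13.7%) under the assumed response rate and arm size. ACR20 is a descriptive key secondary endpoint that is also reported on ITT. The primary endpoint is analysed on the Safety set (SAP 15.1) and does not change.

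Appendix I, which details the exclusion criteria, is not in the text reviewed, so a qualifying condition there cannot be ruled out.

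**What to change.** Before database lock:

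1. Delete the stratification bullet from SAP 10.2.3, and the matching entry, if any, from Appendix I.
2. Keep these patients in the per-protocol set with the corrected stratum value, as SAP 10.2.2 does for ITT.
3. List stratification errors by arm and direction, classed as deviations that are not clinically important in the SAP 10.1 sense. Note any biologic-experienced patient randomised beyond the 20% cap through miscoding.
4. Leave the entry-criteria exclusion in place, so that patients who breach the prior-biologic criterion are still removed. Confirm in Appendix I that inclusion criterion 6 counts as a key criterion.

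The cost is one deleted line and one short listing. The downside is small: a few patients who bypassed the cap may remain in the set, and the listing will show them.
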